with 10 or more years of military service. Females do not tend to demonstrate coronary artery calcium in the same manner/degree as males. Therefore an additional pilot sample of 30 female volunteers will be used to assess the prevalence detected in the female active duty population.

Data Analysis

- Primary Aims:
 - Determine prevalence of atherosclerosis in active duty enlisted military members with 10 or more years of military service using coronary artery calcium scoring.
 - A 95% confidence interval will be calculated for the observed prevalence in the active duty population.
 - Assess the rate of reclassification of subjects from one risk category using Framingham Risk Scores (FRS) to another risk category using the results of the Coronary Artery Calcium (CAC) score.
 - For the purposes of this study, the SHAPE guidelines will be used to classify the CAC scores and percentage by age into the following categories:
 - Low Risk: CAC of 0 and no cardiovascular risk factors
 - Low-Moderate Risk: CAC of 0 with cardiovascular risk factors
 - Moderate-High Risk: CAC 1-100 *and* percentile for age <75%
 - High Risk: CAC 100-399 *or* percentile for age >75%
 - Very High Risk: CAC >100 *and* percentile for age >90% *or* CAC >400
 - For the purposes of this study, the FRS percentages will be classified into the following categories:
 - Low Risk: FRS 0-10%
 - Moderate Risk: FRS 11-15%
 - Moderate-High Risk: FRS 16-20%
 - High Risk: FRS >20%
 - Very High Risk: Acute Coronary Syndrome or known Coronary Artery Disease or significant multiple risk factors

This study will assess the rate at which CAC scoring reclassifies the FRS of a subject to a different risk category. To do so a descriptive table will be used to demonstrate the changes seen. The net reclassification improvement (NRI) will be calculated to describe further the amount of reclassification that is accomplished by using the CAC scoring method (19). Please see reference 19 for more information.

- Compare the Framingham Risk Score (FRS) to the Coronary Artery Calcium (CAC) score for enlisted subjects with at least 10 years of military service to determine how well the results correlate with one another.

- Linear Regression model will be used to determine if the FRS score correlates with the CAC score.
- Secondary Aims:

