6.7. Subject Population

Age Range: ≥ 18 y/o Children (< 18)

Sex: Male Female

Vulnerable Population: No Yes (explain)

- Children, pregnant women, fetuses, neonates, mentally disabled, and prisoners will not be used in this research study as the population this study is looking at military members with at least 10 years of service. Any females identifying that they may be pregnant will be excluded from the study.

Number of Subjects:

- Total Number of Subjects (nation-wide/study-wide): 180
- Number of Subjects Planned for DGMC: 180
- Number of Subjects Planned for (Specify Institution): 0

Inclusion/Exclusion Criteria:

- **Inclusion Criteria:**
 - Active Duty Military Members with at least 10 years of service
 - Enlisted Rank
 - Males 35 years and older OR Females 45 years and older (please note the age difference is due to the fact that female plaque formation with calcification has been shown to lag that of males by about 10 years)
 - One or More of the Following Risk Factors:
 - **Smoker** – at least 5 pack years in the past 5 years (pack year = number of packs per day * number of years of smoking)
 - **Diabetic** (Fasting glucose of >125 mg/dL on two or more blood draws, or Random Blood Glucose of >200 mg/dL on a single blood draw, or HgbA1C >6.5%, or previous diagnosis of diabetes listed in the subject's medical record) or **Pre-diabetic** (Fasting glucose >100 on two or more blood draws or HgbA1C 5.7-6.4)
 - **Hypertension** (SBP > 140 or DBP >90 or on blood pressure medications or diagnosis of hypertension in medical record)
 - **Waist Circumference** > 40 inches for males or >35 inches for females
 - **Hyperlipidemia** (LDL >130, HDL <40 for males, HDL <50 for females, Triglycerides >200, on lipid lowering medications and/or diagnosis of hyperlipidemia in medical record)
- **Exclusion Criteria:**

- Males <35 years old
- Women <45 years old (please note the age difference is due to the fact that female plaque formation with calcification has been shown to lag that of males by about 10 years)
- Officer Rank – officers are excluded as we are looking at the enlisted culture in the military.
- History of any of the following:
 - Coronary Artery Disease (CAD)
 - Coronary Artery Bypass Grafting (CABG)
 - Myocardial Infarction (MI)
 - Percutaneous Intervention/Stent Placement (PCI)
 - Angina – cardiac chest pain
 - Radiotherapy (external beam, brachytherapy, radiopharmaceutical)

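### Primary aim 2: no eligible subject can fall in the lowest CAC category, so everyone classed FRS Low counts as reclassified upward, even with a calcium score of 0

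*Combined protocol and SAP*

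**What the plan says.** Section 6.6 (Data Analysis, Primary Aims) defines the output of aim 2: "This study will assess the rate at which CAC scoring reclassifies the FRS of a subject to a different risk category". A descriptive table and a net reclassification improvement (NRI) are to present it.

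The two lowest CAC levels are "Low Risk: CAC of 0 and no cardiovascular risk factors" and "Low-Moderate Risk: CAC of 0 with cardiovascular risk factors". Above them come Moderate-High, High and Very High, set by CAC score and age percentile.

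The lowest FRS level is "Low Risk: FRS 0-10" percent, with no condition on risk factors. Next come 11-15% (Moderate), 16-20% (Moderate-High) and above 20% (High). The top level is "Very High Risk: Acute Coronary Syndrome or known Coronary Artery Disease or significant multiple risk factors".

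The inclusion criteria in section 6.7 require "One or More of the Following Risk Factors": smoking, diabetes or pre-diabetes, hypertension, waist circumference or hyperlipidemia. The aims in section 6.2 call these cardiovascular risk factors. Section 6.7 also gives "Total Number of Subjects (nation-wide/study-wide): 180".

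The background in section 6.1 likewise places zero calcium with risk factors one step above the lowest risk. It labels FRS 11-15% low-moderate, which makes that band the natural partner of CAC Low-Moderate.

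**The concern.** The entry criterion closes the lowest CAC level to everyone enrolled, while the lowest FRS level stays open. The two scales cannot agree at FRS Low. A subject with FRS 4% and no detectable calcium is counted as moved to a higher risk level, although section 6.1 credits a zero score with a 99% negative predictive value. That move comes from eligibility and category wording, not from the scan.

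The reclassification rate is the stated result of a primary aim, and the distortion runs toward the hypothesis in section 6.2 that CAC shows more risk than FRS. Section 6.6 gives that hypothesis no formal test, so the descriptive rate carries much of the message. The NRI would presumably use the same levels.

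The same definitions have two smaller faults. The top FRS level rests partly on conditions excluded at entry (known CAD, MI, angina) and partly on an undefined phrase about multiple risk factors, which could pull a subject out of any FRS level. The CAC bands also overlap and leave gaps.

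**Working it through.** **The plan's own figure.** The plan states no expected reclassification rate. The related figure is the sample size in section 6.6: n = 1.96² × p(1 − p) / 0.05². This gives 119.5 at p = 8.5% (plan: 120) and 138.3 at p = 10% (plan: 138). It reproduces, and it supplies the 10% prevalence used below.

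**The floor.** Let f be the share of subjects classed FRS Low and p the share with CAC above 0.

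- CAC Low needs zero risk factors and eligibility needs at least one, so P(CAC Low) = 0.
- A subject classed FRS Low can reach only CAC Low-Moderate, Moderate-High, High or Very High. All lie above Low.
- Hence the upward rate is at least f for any set of scan results, and equals f if every CAC is 0.
- Downward moves need FRS of 16% or more, or assignment to FRS Very High, so the downward share is at most 1 − f. If f exceeds 50%, the net direction is upward whatever the CT shows.

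**Size.** The documents do not give f. Section 6.4 says only that some subjects may have FRS below 5%, so 50, 70 and 90% are assumptions. With p = 10% and the same prevalence at every FRS level (also an assumption):

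- Up as written: from f to f + p(1 − f). The range reflects how many of the remaining subjects can move up.
- Part that is FRS Low with CAC 0: f(1 − p). Without the equal-prevalence assumption it lies between f − p and the smaller of f and 1 − p.
- Up on the three-level scale described under the fix: from p × f to p.

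| Assumed f | Floor, of 180 | Up as written | Of which FRS Low with CAC 0 (bounds) | Up on three-level scale |
|---|---|---|---|---|
| 50% | 90 | 50-55% | 45% (40-50%) | 5-10% |
| 70% | 126 | 70-73% | 63% (60-70%) | 7-10% |
| 90% | 162 | 90-91% | 81% (80-90%) | 9-10% |

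Section 6.1 also cites 20.6% prevalence in Army men. At p = 20.6% the as-written rates are 50-60.3%, 70-76.2% and 90-92.1%. The three-level rates are 10.3-20.6%, 14.4-20.6% and 18.5-20.6%.

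**Counter-case.** With f = 30%, the other 70% at FRS 16-20% and p = 10%, the upward rate is 30-37% and the downward rate is 0.70 × 0.90 = 63%. The floor remains, but the net direction is down.

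**Band check, section 6.6 rules as written.**

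- Two bands at once: CAC 100 below the 75th percentile (Moderate-High, and "High Risk: CAC 100-399"); CAC above 100 with percentile above 90, and CAC above 400 with percentile above 75 (both High and Very High).
- No band: CAC 400 at or below the 75th percentile; CAC 1-99 at exactly the 75th percentile.
- Section 6.1 starts the High band at 101, section 6.6 at 100.

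**The case against.** The strongest reply is that the effect equals f and f is unknown. It depends on who enrols and on how the multiple-risk-factor phrase is applied, and a low f can leave the net direction downward. This is correct, and it limits what can be said about size. It does not remove the floor, which holds at any f.

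A second reply is that the planned table will expose the problem. If it cross-tabulates FRS by CAC, the Low-Moderate column holds exactly the zero-calcium subjects and a reader can subtract the FRS-Low cell. No data are lost, and aims 1 and 3 do not use these levels. That also stands. But the plan nowhere says this cell is not reclassification, so the reported rate would include it.

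Third, the counts use all 180 recruits. If the expected 10% non-completion applied to everyone, 162 would remain and the floors would be about 81, 113 and 146. A single 10% prevalence is also applied to men and to the 30-woman pilot. These change the illustrations, not the argument.

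Fourth, the three-level scale is one choice among several. When most subjects have FRS of 15% or less, its upward rate comes close to the aim 1 prevalence. Pairing CAC 0 with FRS Low alone would also remove the floor, but FRS 11-15% with CAC 0 could then count as a downward move. This is a fair point, and it is why the full cross-table should be reported too.

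Finally, the overlaps and gaps concern either cases that a take-the-highest-band rule would settle or exact edge values, so few subjects are likely to be affected. They are drafting faults and do not carry the main point.

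**Conclusion.** The concern holds. Sections 6.6 and 6.7 together make agreement at FRS Low impossible and set a floor of f under the upward reclassification rate, whatever the scans show. Nothing in the available text corrects this; the attachments and flow chart could not be read. The logic needs no outside figure.

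The size rests on assumed f. For f of 50-90% and 10% prevalence equal across FRS levels, the upward rate is 50-91% as written, against 5-10% when zero calcium cannot count as an upward move. Two statements hold without the equal-prevalence assumption: the as-written rate is at least f, and the corrected rate is at most the share with CAC above 0. The direction favours the study hypothesis. As written, the aim 2 rate mixes a product of the definitions with the effect of the scan, so the definitions should be changed before analysis.

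**What to change.** Amend the category definitions in section 6.6, for the aim 2 comparison only:

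1. Pre-specify three levels on which agreement is possible throughout. Level 1: CAC 0 paired with FRS 0-15%. Level 2: CAC Moderate-High paired with FRS 16-20%. Level 3: High and Very High merged on both scales.
2. Assign the FRS level from the percentage alone, or define the multiple-risk-factor phrase objectively before analysis.
3. Assign CAC bands in a fixed order so that each subject has exactly one: CAC 0; then Very High (CAC above 400, or above 100 with percentile above 90); then High (any remaining CAC above 100, or percentile 75 or more); then Moderate-High (all remaining CAC above 0).
4. Reconcile the CAC cut-points and the FRS 11-15% label between sections 6.1 and 6.6.
5. Report the full uncollapsed FRS by CAC cross-table alongside, so that the SHAPE levels stay visible and other pairings can be examined. If the NRI is kept, state which levels it uses.

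The cost is a text amendment with no new data. The follow-up rules in section 6.4 use their own CAC cut-points and are not touched. The scale is coarser and departs from the SHAPE levels for this one comparison. The reported upward rate will be lower, for example 9-10% instead of 90-91% at 10% prevalence and assumed f of 90%.

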The FRS was developed by Wilson et al in 1998 and has become standard of care for estimating risk of a cardiovascular event over the next 10 years. The estimation takes gender, age, smoking status, systolic blood pressure, total cholesterol and HDL into account when predicting risk (4). Scores are converted into percentage of risk over the next 10 years using a table created by Wilson et al. Individuals with scores of 0-10% are considered low risk. A score of 11-15% indicates low-moderate risk, while a score of 16-20% indicates mod-high risk. Those with scores of >20% are considered high risk, while those with known coronary artery disease or acute coronary syndrome are considered very high risk (2). While the FRS at times is a basis for treatment decisions, this system of calculating risk is not individualized, and does not take into account other contributing factors such as family history, weight, etc.

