 - A focus of coronary calcium will be defined as the presence of four or more contiguous pixels with >130 Hounsfield units. Total and per-vessel (right coronary artery, left main coronary artery, left anterior descending branch and left circumflex branch) CAC burden will be assessed by the cardiac radiologist using the Agatston scoring method.
- **Follow-Up:** Scan results with CAC scores will be read within 10 days after the CT scan. The research coordinator or other study team member will be alerted

when results are placed in CHCS. When results are available, the research coordinator will review the results. Follow-up plan will depend on CAC score:

- **For CAC score of zero (0):** Subject will be informed of their score via a results letter that explains the meaning of the score, explains their Framingham Risk Score and provides results of the initial lab work that was drawn (See attachment 7 – Results Letter). These letters will be produced on an individual case basis and mailed to study subjects. If subjects in this category are noted to have abnormal HgbA1C and/or lipid panel their primary care manager (PCM) will be notified of abnormal results via encrypted e-mail.
- **For CAC scores of 1-400:** The study coordinator or other research team member will place a consult/referral into CHCS to the Metabolic Clinic with the words “CAC results follow-up” in the description section. At this time a telephone-consult will be placed in the subject’s AHLTA record (See attachment 8 – Telephone Consult Template) and their PCM will be notified via an encrypted e-mail of the subject’s CAC results and their referral to the metabolic clinic (See attachment 9 – PCM Notification E-Mail Template). If subjects in this category are noted to have abnormal HgbA1C and/or lipid panel their primary care manager (PCM) will be notified of abnormal results via encrypted e-mail. The Metabolic Clinic will see these referrals and have the HL&VC receptionist call the subject to directly schedule a follow-up appointment. The follow-up appointment will be within 60 days of the CAC scan. If subjects fail to attend their follow-up appointment, they will be contacted by a member of the study team to remind them of the importance of following up. The research coordinator will ensure subjects attend follow-up as scheduled, and will document whether they have followed up in the subject’s study chart. At the follow-up appointment, the following will be discussed:

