- Subject will undergo one cardiac CT scan. Appointment for scan will take 10-20 minutes, the majority of which will be subject check in and positioning. Average radiation exposure for a CAC CT is 0.89 millisieverts (mSv). For context, the average population radiation exposure from background is approximately 3.11 mSv at sea level (4.5 mSv at high altitude), meaning

For Protocol Office use only:

Protocol title: Assessment of Coronary Artery Calcium in Active Duty
Enlisted Military Members with 10 or More Years of Service
FDG20130024H Protocol v15 w Amend 9

[figure not shown]
name redacted 6Feb20

DGMC Human Research Protocol

that the dose from this study is less than half of a person's baseline annual dose from sources such as cosmic radiation. Furthermore, a mammogram is approximately 0.73 mSv.

- **Incidental Findings:** As per usual radiology operating procedure, all cardiac CT scans will be reviewed in their entirety for any abnormalities. The report will be placed in CHCS/AHLTA and can be reviewed by the subject's primary care physician. The radiologist reading the films will also make follow-up recommendations for any concerning abnormal findings. The abnormalities will be brought to the attention of the provider who orders the cardiac CT. That provider will then inform the PI or AI of any abnormal findings. The PI/AI will then inform the subject of these findings as well as the follow-up recommendations of the radiologist. An encrypted e-mail will be sent to the subject's primary care physician if incidental findings are discovered.

Study Flow Chart (displayed on following page):

6.6. Data Collection/Analysis:

Sample Size/Power Analysis

- Based on an 8.5% expected prevalence of atherosclerosis in the active duty military population, the sample size requirement for a 95% confidence interval for a proportion of +/- 0.05 is 120 subjects. As the prevalence among active duty with >10 years of military service and at least one cardiovascular risk factor is likely higher, for this study the estimated prevalence is 10%. The sample size requirement for a 95% confidence interval for a proportion +/- 0.05 with a prevalence of 10% is 138 subjects. For this study, anticipated failure of completion/drop out is estimated to be approximately 10%, so 150 male volunteers will be recruited to achieve this confidence interval for prevalence of active duty atherosclerosis in enlisted members

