- **Benefits Outweigh the Risks:** This study will provide subjects with their Coronary Artery Calcium score. This score helps establish a risk score that indicates a more personalized/individualized likelihood of a cardiovascular event in the future. By informing the subject of their risk score and having a results letter sent or counseling session reviewing their results, they are able to better understand what interventions/lifestyle modifications can be completed to potentially decrease their risk of a cardiovascular event in the future. This study can also provide the military with information about the prevalence of atherosclerosis in enlisted members with 10 or more years of service, which could assist public health and the military in making policies/influencing the military culture to promote healthy changes that decrease the risk of atherosclerosis.

6.9. Safeguards for Protecting Subjects:

- This study involves greater than minimal risk to subjects as it involves the exposure to radiation during a CT scan. Primary monitoring of the study will be performed by the study team, who will review accrual and any adverse events on a real-time basis. The study team will ensure that all eligibility criteria and consent requirements are met prior to a subject's participation in the study and that all study procedures and adverse event reporting occur according to the IRB approved protocol. Potential adverse events and risk factors for this study are specifically listed in section 6.8 within this protocol and will be discussed with subjects prior to enrollment. Any event will be graded by severity and outcome. Study staff will make certain that all adverse events are recorded and reported according to AFI 40-402 and SGSE Operating Instruction 40-402-01. Cumulative adverse events will be reviewed monthly. The study team with the advisement of the medical monitor and IRB will make decisions regarding cessation of accrual, and whether or not to close the study on the basis of frequency or severity of Unanticipated Problems Involving Risk to Subject or Others (UPIRSOs), and/or Serious Adverse Events (SAEs). Any deviation, cessation in accrual or early study close will be communicated to the IRB immediately.
- All subjects will be treated in compliance with AFI 40-402 and applicable FDA and DHHS guidelines.

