 - **Exposure to Radiation:** The radiation exposure risk is equivalent to 24 chest x-rays, and is approximately ½ of the background radiation the subject would be exposed to in a year. While the radiation dose cannot be decreased, the CT protocol is designed to run the scan with as few slices/as little radiation exposure as is necessary to obtain the required images. All females who may be pregnant or are pregnant at the time of expressing interest in participation will be excluded from this study.
 - **Emotional Response to/Stress Due to Results:** Some subjects may have results that indicate a high risk of a cardiovascular event in the future. This news could be emotionally stressful to the individual. Subjects will be provided with the study coordinator's phone number which they can call during business hours if they are feeling overwhelmed by the results of their test. The DGMC ER is also available 24

hours a day. The study coordinator will offer information about mental health services available at Travis Air Force Base if requested.

- **Impact on Future Insurance:** Subjects who later separate from the military may not continue to receive TriCare benefits and may have increased civilian insurance premiums and/or difficulty obtaining civilian insurance if this study determines they have coronary artery disease, even if they are asymptomatic. There is no way to decrease this risk, but subjects can opt to not participate in this study if they are concerned about impact on future insurance.
- **Risks of blood draw:** Infection, bleeding, discomfort, bruising. These risks are decreased by using sterile needles, cleaning the skin prior to blood draw and pressure applied after withdrawing the needle.
- **PCM Notification:** Primary care physicians will be notified of all CAC scores >0 via an encrypted e-mail that includes follow-up recommendations (See attached PCM Notification E-Mail Template). A telephone consult note will also be entered in AHLTA with CAC score results. Any abnormal HgbA1C or lipid panel labs will be brought to the attention of the PCM via encrypted e-mail.
- **Data Monitoring:** Data will be monitored monthly by the PI and study staff to identify any adverse events, and to ensure all subjects who underwent cardiac CT scan and CAC scoring attended all recommended follow-up, to include a results letter, follow-up in metabolic clinic, OR follow up in cardiology.

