- **Stop Rules:** No stop rules are anticipated. As this is an observational study looking partly at prevalence of atherosclerosis in enlisted military members with 10 or more years of service, the study team does not anticipate stopping the study early. However if interim statistical analysis shows a prevalence of atherosclerosis = 0, then the principle investigator may stop the study.

7. Conflict of Interest

No conflicts of interest have been identified by any of the research team members.

8. Collaborative Efforts

No collaboration with other facilities will be pursued at this time.

9. Investigation Schedule

	Mar-Apr 2013	May 2013-Nov 2013	Nov 2013-Nov 2016	Nov 2013-Nov 2016	Nov 2013-Nov 2016	Nov 2013-Dec 2016	Dec 2016	Dec 2016-Mar 2017
IRB Approval	X	X						
Surgeon General Approval		X	X					

Recruitment			X	X				
Enrollment			X	X	X			
Baseline Data			X	X	X			
Testing			X	X	X			
Data Collection			X	X	X	X		
Statistical Analysis					X	X	X	
Publications/Reports						X	X	X

Estimated Date of Investigation Beginning: 01 August 2013

Estimated Date of Completion: 30 December 2016

10. Use of Investigational Drug(s) No Yes
 No investigational drugs will be used in this investigation.

11. Use of Investigational Device(s) No Yes
 No investigational devices will be used in this investigation.

12. Support Required

Lab Support:

Request CLIA certificates from all non-DGMC laboratories for your files.

Test Name	Standard Care?	Which lab will perform each test?	Support letter attached?
HgbA1C	Yes and No	DGMC	Yes
Lipid Panel	Yes and No	DGMC	Yes

** Note: Some of these labs will be standard of care if the subject is diabetic and/or has hyperlipidemia and has not had labs drawn in the past 3 months. Those without these diagnoses will have these labs drawn for research purposes only.
 See attachment 16 – Letter of Support – DGMC Lab

Radioactive Materials or Radiology Support:

If radioisotopes or radiation-producing equipment will be used, describe here.

Procedure	Standard Care?*	Which facility will perform proc.?	Support letter attached?
Cardiac CT	No	DGMC	Yes

See attachment 17 – Letter of Support – Radiology

* Any Radiation exposure that is not standard care requires Radiation Safety Committee review.
 See attachment 18 – Radiation Safety Committee Approval

Nursing/Technician Support:

N/A

CIF Support:

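### The net reclassification improvement planned for primary aim 2 needs a cardiac-event outcome, and the plan defines no event endpoint or event-observation period

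*Combined protocol and SAP*

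**What the plan says.** Primary aim 2 (section 6.2) is to assess how often subjects change risk class when CAC replaces FRS. Section 6.6 gives it two analyses: a descriptive table of the changes, and then "The net reclassification improvement (NRI) will be calculated to describe further the amount of reclassification". For the NRI it refers the reader to reference 19.

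Other parts of the protocol that bear on this:

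- **Horizon of the score.** Section 6.1 describes the FRS as "estimating risk of a cardiovascular event over the next 10 years".
- **Procedures.** Section 6.5: "Subject will undergo one cardiac CT scan". The measurements in section 6.4 and the research-material table in section 6.6 contain no cardiac event.
- **Follow-up (section 6.4).** For CAC 0: "Subject will be informed of their score via a results letter". For CAC 1-400: "The follow-up appointment will be within 60 days of the CAC scan". For CAC above 400, a cardiology visit is also due no later than 60 days after the scan.
- **Safety monitoring (section 6.9).** "Potential adverse events and risk factors for this study are specifically listed in section 6.8 within this protocol". The monthly data check is whether subjects "attended all recommended follow-up, to include a results letter, follow-up in metabolic clinic, OR follow up in cardiology".
- **Eligibility (section 6.7).** At least one cardiovascular risk factor is required. Known coronary disease, infarction, bypass, stenting and angina are excluded.
- **Schedule (section 9).** Estimated start is 01 August 2013. "Estimated Date of Completion: 30 December 2016".

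**The concern.** The NRI asks whether a new tool moves people who go on to have events up, and people who do not have events down. It measures predictive improvement against a known outcome. It does not measure how much reclassification occurs, which is the use section 6.6 gives it. Without event status it has no value.

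The risk is that a number is produced anyway, from an invented or incidental event status, and reported as an improvement in prediction. The study summary ahead of section 5 says CAC scoring may be used to stratify this population if it is shown to be more accurate. A figure labelled improvement would look like evidence for that, and these data cannot provide it.

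The table that remains has a weakness of its own. The CAC Low class requires no risk factors, yet every eligible subject has at least one. A large part of the upward movement could then come from class labels and not from scan results, in the direction of the section 6.2 hypothesis.

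**Working it through.** **1. The plan's own arithmetic.** The only sizing is for prevalence. With n = 1.96² × p(1 − p) / 0.05², p = 0.085 gives 119.5 (stated 120) and p = 0.10 gives 138.3 (stated 138). Both reproduce. Neither concerns the NRI, for which the plan states no figure.

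**2. What the NRI needs.**

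NRI = [P(up | event) − P(down | event)] + [P(down | non-event) − P(up | non-event)]

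With no recorded events the first bracket has a zero denominator, and the NRI is undefined.

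**3. The table alone does not determine the NRI.** Assume 162 subjects (180 × 0.90; the 10% dropout is stated for men and assumed for all), with 60 moved up and 10 moved down. Suppose 5 subjects had events:

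- All 5 among those moved up: 5/5 − (55 − 10)/157 = +0.71.
- All 5 among those moved down: −5/5 − (60 − 5)/157 = −1.35.

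The same table gives either sign, depending only on who had events.

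**4. Could adverse-event reports supply events?** Expected events = 162 × [1 − (1 − r)^(60/3652.5)], with a constant hazard, a 60-day window for everyone and assumed 10-year risk r:

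| r | Expected events | Chance of none |
|---|---|---|
| 2% | 0.05 | 95% |
| 5% | 0.14 | 87% |
| 10% | 0.28 | 76% |
| 20% | 0.59 | 55% |

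The whole calendar span from estimated start to completion is 3.41 years, against the 10-year horizon of the FRS. Following every subject for a full 3 years, which is not planned, would give about 1 event at r = 2% and 10.5 at r = 20%.

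**5. Class matching in the table.** Let s be the share classed FRS Low (0-10%) and p the proportion with CAC above 0 in that group. If the lowest classes are kept separate, each FRS Low subject with CAC 0 counts as moved up to Low-Moderate. If FRS 0-15% is merged and set against CAC 0, that subject is unchanged. The difference in percent moved up is s(1 − p). Percent moved down is the same either way, because no subject can be in CAC Low.

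| p | s = 50% | s = 95% |
|---|---|---|
| 10% (prevalence assumed in section 6.6) | 45 points | 86 points |
| 20.6% (male figure cited in section 6.1) | 40 points | 75 points |

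The exception is a subject placed in FRS Very High through its clause on multiple risk factors, which is not defined.

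**6. Precision of the replacement, after merging.** Moving up then requires CAC above 0, so percent up cannot exceed prevalence. The half-width for percent up is 1.96 × √(p(1 − p)/n). For net movement (up share u, down share d) it is 1.96 × √((u + d − (u − d)²)/n).

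| Quantity | Prevalence 10% | Prevalence 20.6% |
|---|---|---|
| Percent up, at most (n = 162) | 10% ± 4.6 | 20.6% ± 6.2 |
| Half-width for percent up, men only (n = 150 × 0.90 = 135) | ± 5.1 | ± 6.8 |
| Net, at most, with 5% moved down (assumed, n = 162) | +5.0 ± 5.9 | +15.6 ± 7.4 |

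**The case against.** - **The NRI is supplementary.** The table is the main method for aim 2, and no sample-size or stopping decision uses the NRI. This stands and limits the damage. It does not make the statistic calculable.
- **Reference 19 supplies the method.** A citation can supply a formula. It cannot supply outcomes for these subjects.
- **Another outcome could serve.** Using CAC above 0 as the event would be circular, because CAC defines the new classes. A version based on expected risk would need event probabilities for the CAC classes, and the plan gives none. Adverse-event reporting might pick up a heart attack during participation, but it is safety monitoring, and the risks listed in section 6.8 include no cardiac event.
- **A horizon is stated.** Ten years is the horizon of the scores. What is missing is a period over which events are observed. The 3.41 years is a calendar span, not follow-up per subject.
- **Classes can be matched by name and order.** That is a natural reading, and merging departs from the classes the plan adopts. So both versions should be shown. The empty CAC Low class remains a fact under either reading. Class matching is a separate defect of the table, and its size does not measure the NRI problem.
- **The illustrations are not fully consistent.** This is fair. An average 10-year risk of 20% cannot coexist with 95% of subjects at 10% or below: the other 5% would need risks of at least (0.20 − 0.95 × 0.10)/0.05 = 210%. The 60-day window is generous for CAC 0 subjects, who receive only a letter. The 20.6% is a male figure; with 4.3% for women (section 6.1), 135 men and 27 women average 17.9%. Overall prevalences also stand in for the prevalence among FRS Low subjects. None of this supplies the missing outcome.

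**Conclusion.** The concern holds. A statistic named for a primary aim cannot be validly produced from the planned data, because the plan defines no cardiac-event endpoint, event definition or observation period. This follows from the NRI formula and the protocol's own procedures, without any numerical assumption.

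The consequence is bounded: aim 2 is still answered by the descriptive table, and the prevalence aim is untouched. What must not happen is that a number called improvement is reported.

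The table needs its class matching fixed in advance. The choice shifts percent moved up by roughly 40 to 86 points over the ranges shown. That range rests on assumed values of s and p, which the documents do not give for this population; the event counts likewise rest on assumed 10-year risks.

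**What to change.** In section 6.6:

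1. Delete the NRI sentence and keep the descriptive FRS-by-CAC table.
2. Report percent moved up, moved down, unchanged and net (up minus down) with 95% confidence intervals, overall and by starting FRS class. These also describe the direction stated in the section 6.2 hypothesis; no sign test is required.
3. State in advance how the lowest classes are matched, and show results with them separate and with them merged (FRS 0-15% against CAC 0).
4. Before counting, define the multiple-risk-factor clause of the FRS Very High class.
5. State how the CAC class edges are handled. As section 6.6 is written, CAC 100 can fit two classes (section 6.1 starts the higher band at 101), CAC 400 below the percentile cut-offs fits none, and High overlaps Very High.
6. Conclude only that the two tools assign different risk classes, not that CAC is more accurate or improves prediction.

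Keeping an NRI would instead require a defined event endpoint, ascertainment and adequate follow-up, which would be a different study.

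The cost is wording and two versions of one table, with no new data or subjects. The study gives up a claim of improved prediction that its data could not support. Intervals outside the lowest FRS class will be wide: in a class of 8 (5% of 162, assumed), 4 of 8 moved has an exact 95% interval of 16% to 84%, and 8 of 16 has 25% to 75%.
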